## 9.1 Analysis of the primary pharmacokinetic variables

The primary PK variables in plasma used for EE and LN are  $C_{max}$  and AUC.  $C_{max}$  and AUC will be determined from the observed concentration and time data. AUC will be computed using the linear up/log down trapezoidal rule.

The PK individual time plasma concentrations and the primary PK parameters of EE and LN will be summarized by treatment (PSL+OC/OC alone), using descriptive statistics (number of available observations [n], arithmetic mean, median, standard deviation, minimum, maximum, geometric mean, geometric CV and 95% CI for the geometric mean [assuming log-normally distributed data]). Values below the LLOQ will be reported with a clear sign (flag variable in the dataset) indicating that they were below the LLOQ.

Individual study participant concentration-time profiles of EE and LN will be displayed graphically on both linear and semi-logarithmic scales. Spaghetti plots will be presented for all study participants per treatment (OC alone and PSL+OC) and analyte with all study participants overlaid on the same plot (linear and semi-logarithmic scale). Ping-pong plots will also be produced for  $C_{max}$  and AUC for EE and LN (with and without PSL).

The EE/LN primary PK parameters will be compared between treatments (PSL + OC and OC alone) using analysis of variance for a cross-over design (treatment, period, sequence as fixed effects, and subject within sequence as random effect) on the log-transformed parameters and estimation of the geometric mean ratio of PK parameters between treatments with their 90% CI will be provided.

A lack of PSL effect on EE/LN will be concluded if the 90% CI of the geometric mean ratio between treatment PSL+OC and treatment OC alone of the least squares means for the log-transformed AUC, and  $C_{max}$  is within the bioequivalence acceptance range of 80% to 125%.

If the 90% CI is slightly broader than the bioequivalence criteria, individual AUC and  $C_{max}$  geometric mean ratios will be assessed with the aim of achieving  $>0.7$  (less than a 30% decrease in OC exposure in the presence of PSL) to declare a lack of a clinically significant PK interaction.

Geometric mean profiles of plasma concentrations for EE and LN over time will be presented, with both treatments (PSL+ OC and OC alone) overlaid on the same plot, in both linear and semi-logarithmic scale. For the linear scale plot only, the lower and upper 95% confidence interval (CI) for the geometric mean will be displayed.

All plasma concentration figures will include the LLOQ on the semi-logarithmic scale plots and will be based on scheduled times.

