4.2 Scientific rationale for study design

The potential interaction between PSL and OC will be assessed with a two-way cross-over study design, which is deemed appropriate to reach the goal of the study.

In Part 1, PSL will be up-titrated from 100mg to 400mg BID over 5 days and, in Part 2, from 100mg BID to 200mg BID in 1 day to increase tolerability as demonstrated in previous clinical

pharmacology studies. Afterwards, a steady-state period of 7 days will take place before subjects receive OC. This 7-day steady-state period will ensure that the potential CYP3A4 induction (mediated by PSL) is close to its maximum level and will be appropriate to evaluate the effect on OC. After OC administration, PSL will be tapered.

The washout period between the 2 treatment periods has a duration of 14 days mainly to ensure that CYP3A4 enzyme activity is back to baseline.

Since the risk of DDI between OC and PSL is predicted to be low (PSL 400mg BID) or not clinically relevant (PSL 200mg BID) and to reduce the burden of continuous administration of PSL (over 2 menstrual cycles) at the MTD in healthy female study participants, the DDI potential of PSL will be assessed on a single dose of the chosen OC. Therefore, EE and LN PK parameters (C_{max} and AUC) will be used as primary endpoints and bioequivalence criteria will be applied for defining clinical relevance of the DDI (). This PK-based approach has been used widely to assess DDI between OC and many drugs (Menon et al, 2016; Mohamed et al, 2018; Hurst et al, 2016; Crawford et al, 1990; Mildvan et al, 2002).

This study design will also allow evaluation of the effect of single dose OC on the steady-state PK of PSL and its metabolites.

Single dose OC is deemed appropriate to investigate the potential effect of EE/LN on PSL as there is no accumulation described with EE (Kuhnz et al, 1994). Though LN is known to accumulate (2 to 3-fold) following repeated administration (Kuhnz et al, 1994), there have been no CYP3A4/2C19 inhibition effects described in the literature (Palovaara et al, 2003); therefore, no DDI mediated by LN is expected.

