9.3 Planned pharmacokinetic analyses

All PK analyses will be performed using the PK-PPS. Pharmacokinetic parameters of EE, LN, PSL, and PSL metabolites (eg, C_{max} , t_{max} , AUC or AUC_{0-t} or AUC_{τ} , $t_{1/2}$ or CL/F) will be estimated using noncompartmental analysis with Pharsight Phoenix[®] WinNonlin[®] v6.3 (or higher) software. Pharmacokinetic analyses will be performed and reported for each study part (Part 1 and Part 2).

The individual time-plasma concentrations of EE, LN, PSL, PSL metabolites, and PK parameters of EE, LN, PSL and PSL metabolites will be summarized by treatment using descriptive statistics (number of observations, geometric mean, lower and upper 95% confidence intervals [CI], geometric coefficient of variation [CV], arithmetic mean, standard deviation [SD] and CV, median, and minimum and maximum value) and graphical displays.

Ethinylestradiol/levonorgestrel primary PK parameters will be compared between treatments using analysis of variance for a cross-over design (treatment, period, sequence as fixed effects, and subject within sequence as random effect) on the log-transformed parameters and estimation of the geometric mean ratio of PK parameters between groups with their 90% CI will be provided.

Lack of PSL effect on EE/LN will be concluded if the 90% CI of the geometric mean ratio between treatment PSL+EE/LN and treatment EE/LN of the least squares means for the log-transformed AUC, and C_{max} is within the bioequivalence acceptance range of 80% to 125%.

If the 90% CI is slightly broader than the BE criteria, individual AUC and C_{max} geometric means ratios will be assessed with the aim of achieving >0.7 (less than a 30% decrease OC exposure in the presence of PSL) to declare a lack of a clinically significant PK interaction.

Pharmacokinetic parameters ($C_{max,ss}$, AUC_{τ}) of PSL and its metabolites will be compared between days with OC [Part 1: Day 13 for Treatment Sequence A and Day 30 for Treatment

Sequence B; Part 2: Day 9 for Treatment Sequence A and Day 26 for Treatment Sequence B] and without OC [Part 1: Day 12 for Treatment Sequence A and Day 29 for Treatment Sequence B; Part 2: Day 8 for Treatment Sequence A and Day 25 for Treatment Sequence B] using analysis of variance on the log-transformed parameters and estimation of geometric ratio of PK parameters between days with their 90% CI will be provided.

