The relationship between individual AUC ratio (with and without PSL) of EE and LN, and the exposure to PSL (AUC_{τ}) will be assessed by scatterplots and linear regression analyses (log-transformed and also untransformed data).

The estimated slope with 95% CI will be computed. In absence of interaction, intercept and slope will be equal to 0.

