9.9 Determination of sample size

Lack of PK interaction in this study will be concluded if 90% confidence intervals for both AUC and C_{max} geometric means ratios (with/without PSL) of LN and EE are included in the 80% to 125% bioequivalence range.

In a previous OC interaction study conducted by UCB with brivaracetam (N01282), an intra-subject coefficient of variation of 10% for AUC_t for both EE and LN (including C_{max}) and 16% for C_{max} was observed for EE.

Provided that the ratio of the expected means for test (with PSL) and reference (without PSL) is included in the range [0.90, 1.10] and for a type-I error of 0.05 and an intra-subject coefficient of variation of 16%, a total sample size of 34 study participants should allow at least 90% power for the assessment of lack of interaction (or 26 study participants for 80% power).

A total of 40 study participants will be randomized: Part 1 (PSL 400mg BID) will include 14 study participants and will allow a good estimate of the different ratios of PK parameters. Part 2 (PSL 200mg BID) will include 26 study participants (13 study participants in each sequence). Assuming no drop-outs, a decrease of 10% in PK parameters of OC and intrasubject coefficient of variation of 16%, this will allow 80% power for assessing lack of PK interaction.

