## 9.2 Analysis of secondary pharmacokinetic variables

The secondary PK variables in plasma used for PSL are  $C_{max,ss}$  and  $AUC_{\tau}$ .  $C_{max,ss}$  will be determined from the observed concentration and time data.  $AUC_{\tau}$  will be computed using the linear up/log down trapezoidal rule.

Pharmacokinetic parameters ( $C_{max,ss}$ ,  $C_{trough}$ ,  $AUC_{\tau}$ , metabolic ratio based on  $AUC_{\tau}$  ( $MR_{AUC_{\tau}}$ )) of PSL and its two metabolites will be compared between days with OC [Part 1: Day 13 for Sequence A and Day 30 for Sequence B; Part 2: Day 9 for Treatment Sequence A and Day 26 for Treatment Sequence B] and without OC [Part 1: Day 12 for Treatment Sequence A and Day 29 for Treatment Sequence B; Part 2: Day 8 for Treatment Sequence A and Day 25 for Treatment Sequence B] using analysis of variance on the log-transformed parameters and estimation of geometric ratio of PK parameters between days with their 90% CI will be provided. Ping-pong plots will also be produced for each study part for  $C_{max,ss}$ ,  $AUC_{\tau}$ ,  $MR_{AUC_{\tau}}$ ,  $MR_{C_{max,ss}}$ ,  $CL_{ss}$ ,  $t_{1/2}$ , for PSL (with and without OC).

The relationship between individual AUC ratio and individual  $C_{max}$  (with and without PSL) of EE and LN, and the exposure to PSL ( $AUC_{\tau}$ ) will be assessed by scatterplots and linear regression analyses (log-transformed and also untransformed data) presented for each study part.

The estimated slope with 95% CI will be computed. In absence of interaction, intercept and slope will be equal to 0.

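### The fallback for declaring no clinically significant PK interaction has no fixed error rate: the excess over 80–125% has no limit and the 0.7 cut has no confidence bound (minor)

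*SAP*

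**What the plan says.** SAP 9.1 has two tiers. The strict tier concludes a lack of PSL effect when the 90% CI of the geometric mean ratio (PSL+OC over OC alone) lies within 80% to 125%. The second reads "If the 90% CI is slightly broader than the bioequivalence criteria, individual AUC and" Cmax geometric mean ratios will be assessed with the aim of exceeding 0.7 ("less than a 30% decrease in OC exposure in the presence of PSL) to declare a lack of a clinically significant PK interaction"). Protocol 9.3 has the same fallback: "If the 90% CI is slightly broader than the BE criteria, individual AUC and" so on. The Amendment 2 change table gives flexibility of interpretation as the reason for specifying the criteria further.

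The sample-size sections (Protocol 9.9, SAP 2.3) cover only the strict tier: "Lack of PK interaction in this study will be concluded if 90% confidence intervals for both AUC and" Cmax fall in the range. They say that Part 1 "will include 14 study participants and will allow a good estimate of the different ratios of PK parameters", and claim no power for it. Protocol 4.2 says that "bioequivalence criteria will be applied for defining clinical relevance of the DDI", without mentioning 0.7. SAP 1 records that the project was terminated, that reporting is restricted to Part 1, and that only a subset of outputs will be produced.

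**The concern.** The fallback is worded as a route to a declaration, but two things needed to fix its error rate are absent: a limit on *slightly*, and a confidence requirement on 0.7. I found neither elsewhere in the two documents. A point estimate just above 0.7 is compatible with a true ratio well below it. At n=14 and a CV of 16%, an observed 0.71 has a lower 90% limit of about 0.64.

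The fallback is also likely to be needed. Protocol 2.1 predicts a 16% fall in EE AUC at 400mg BID, a ratio of 0.84, and with 14 participants the strict rule usually fails there. If a conclusion is then stated for Part 1, its wording could depend on a reading chosen after the interval is known.

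**Working it through.** **Inputs.** n=14, 7 per sequence (Protocol 1.1.6). Intra-subject CV 16% for EE Cmax and 10% for the other parameters (Protocol 9.9, SAP 2.3, from the sponsor's earlier OC study; its AUCτ value is used for AUC). Type I error 0.05, that is, a 90% CI. Predicted EE AUC ratio 1 − 0.16 = 0.84 (Protocol 2.1). The lower limits of 0.78, 0.75 and 0.70 tried for *slightly* are my assumptions.

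**Reproducing the plan's figure.** For a balanced 2×2 crossover on the log scale, σ = √ln(1+CV²), SE = σ√(2/N), df = N−2. Exact two one-sided tests at ratio 0.90 and CV 16% give 79.99% power at N=24, 82.9% at N=26, 89.4% at N=32 and 91.1% at N=34. The stated 26 (80%) and 34 (90%) are reproduced as the smallest even N.

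**Part 1.** At CV 10%, σ = 0.0998 and SE = 0.0998 × √(2/14) = 0.0377. At CV 16%, σ = 0.1590 and SE = 0.0601. With 12 df, t = 1.782, so the CI multiplies and divides the estimate by exp(1.782 × SE) = 1.070 or 1.113.

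**Strict rule at a true ratio of 0.84.** It passes 33.6% (CV 10%) or 19.0% (CV 16%). At CV 10%, the value for EE AUC, it therefore fails about 66% of the time.

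**Fallback, per parameter.** Simulated with log estimate ~ N(ln R, SE²), variance estimate ~ SE²·χ²(12)/12, and 4,000,000 trials per CV. Every row requires an estimate above 0.70. The lower-limit rows also require the upper limit to be at most 1.25, and they count trials that pass the strict rule.

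| How *slightly broader* is read | True ratio 0.70, CV 10% / 16% | True ratio 0.84, CV 10% / 16% |
|---|---|---|
| Lower limit ≥ 0.78 | 0.001% / 0.04% | 58% / 32% |
| Lower limit ≥ 0.75 | 0.04% / 0.3% | 88% / 55% |
| Lower limit ≥ 0.70 | 5.0% / 5.0% | 99.8% / 89% |
| CI merely overlaps 80–125% | 4.6% / 32% | – |
| No limit at all | 50% / 50% | – |

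The 0.70 column is the false-declaration rate; the 0.84 column shows how often a favourable statement would be made at the predicted EE AUC ratio.

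**Hand check of the overlap row.** The upper limit reaches 0.80 when the estimate is about 0.80/1.0695 = 0.748 or 0.80/1.113 = 0.719. From a true 0.70 these lie ln(0.748/0.70)/0.0377 = 1.76 and ln(0.719/0.70)/0.0601 = 0.44 standard errors away, with upper tails of about 4% and 33%. These agree with the simulation, which also lets the variance estimate vary.

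**The case against.** **Tight readings are safe.** An ordinary reading of *slightly* keeps the lower limit near 0.80, and the error at 0.70 is then 0.3% or less. This stands: the fault is that the plan leaves the reading open, not that every reading inflates error. The 32% needs a loose reading and applies to EE Cmax alone. If all four parameters had to pass and all were truly 0.70, independence would give about 0.046³ × 0.32 = 0.003%. The fallback sentence does not say that all four must pass, and about 32% remains if only EE Cmax falls that far.

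**Little depends on it now.** The project has ended and only a subset of Part 1 outputs is due. That lowers the severity, but it does not withdraw the declaration rule from SAP 9.1.

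**Stronger readings that the documents do not support.** A reader might infer a 50% error rate, but that arises only if *slightly* is ignored. A reader might also take the word individual to mean that every participant must exceed 0.7, since SAP 9.2 has "The relationship between individual AUC ratio and individual" Cmax, and Protocol 9.3 has "The relationship between individual AUC ratio (with and without PSL) of EE and LN, and the exposure to PSL". Those phrases lack the words geometric mean. In SAP 9.1 and the sample-size sections, geometric mean ratio is the group estimate, and no all-participants rule is written anywhere. Finally, a reader might see Protocol 4.2 as contradicting the fallback. Protocol 9.3 can be read as elaborating 4.2, so this is a point to reconcile and not a demonstrated conflict.

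**Conclusion.** The concern holds, at minor severity. The fallback permits a declaration whose error rate the plan does not fix: per parameter, the plausible range at a true ratio of 0.70 runs from near zero to 5%, and a loose overlap reading takes it to 32% for EE Cmax. The strict conclusion keeps its 5% control per parameter. A biased estimate is not at issue, because the ratio and its 90% CI are planned whatever is declared; the possible harm is to the stated conclusion.

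The sizes assume that the CVs from the earlier OC study carry over, that all 14 participants are in the PK Set, and that the data are log-normal. The 0.84 is a prediction for EE AUC only, so the 19% strict pass rate at CV 16% is a sensitivity figure.

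**What to change.** Amend the SAP before database lock, as SAP 1 already provides, and record the change from Protocol 9.3 in SAP 3.9.

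*Preferred:* label the fallback descriptive for Part 1, which is not powered, and make no declaration from it. Cost: there is no second-tier conclusion.

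*If the sponsor keeps a declaration:* state that geometric mean ratio means the group least-squares-mean ratio for each parameter. Require, for AUC and Cmax of both EE and LN, a lower 90% limit above 0.70 and an upper limit of at most 1.25. Report this separately from lack of PSL effect. The error is then 5% per parameter at 0.70.

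This option is stricter than a point-estimate cut: the observed ratio must exceed about 0.70 × 1.070 = 0.75 (CV 10%) or 0.70 × 1.113 = 0.78 (CV 16%). It is looser than a tight reading of *slightly*: at a true ratio of 0.75 it declares 53% (CV 10%) or 29% (CV 16%), against 5% with a lower limit of 0.75. The sponsor would have to accept 0.70 as a margin knowingly.

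Either way, the SAP 3.9 entry should reconcile 0.7 with the Protocol 4.2 statement on clinical relevance. No new data are needed.

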## 2.3 Determination of sample size

Lack of PK interaction in this study will be concluded if 90% confidence intervals for both AUC and  $C_{\max}$  geometric means ratios (with/without PSL) of LN and EE are included in the 80% to 125% bioequivalence range.

In a previous OC interaction study conducted by UCB with brivaracetam (N01282), an intra-subject coefficient of variation of 10% for  $AUC_{\tau}$  for both EE and LN (including  $C_{\max}$ ) and 16% for  $C_{\max}$  was observed for EE.

Provided that the ratio of the expected means for test (with PSL) and reference (without PSL) is included in the range [0.90, 1.10] and for a type-I error of 0.05 and an intra-subject coefficient of variation of 16%, a total sample size of 34 study participants should allow at least 90% power for the assessment of lack of interaction (or 26 study participants for 80% power).

A total of 40 study participants will be randomized: Part 1 (PSL 400mg BID) will include 14 study participants and will allow a good estimate of the different ratios of PK parameters. Part 2 (PSL 200mg BID) will include 26 study participants (13 study participants in each sequence). Assuming no drop-outs, a decrease of 10% in PK parameters of OC and intrasubject coefficient of variation of 16%, this will allow 80% power for assessing lack of PK interaction.

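### The >0.7 fallback has no upper limit and is not confined to the 80% side, so an upper-side breach judged slightly broader can be declared no clinically significant interaction

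*SAP*

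**What the plan says.** SAP 9.1 concludes lack of a PSL effect when the 90% CI of the geometric mean ratio (PSL+OC over OC alone) "is within the bioequivalence acceptance range of 80% to 125" per cent, for AUC and Cmax. SAP 2.3 asks for this for both parameters "of LN and EE are included in the 80% to 125% bioequivalence range". Protocol 4.2 applies bioequivalence criteria to define the clinical relevance of the interaction, and those criteria are two-sided.

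SAP 9.1 then adds a second route, whose entry condition is worded as follows: "If the 90% CI is slightly broader than the bioequivalence criteria, individual AUC and". The second parameter named there is Cmax. The check itself is that the "geometric mean ratios will be assessed with the aim of achieving" a value above 0.7, which the SAP glosses as "less than a 30% decrease in OC exposure in the presence of PSL) to declare a lack of a clinically significant PK interaction". Protocol 9.3 carries the same rule with the same value of 0.7: "If the 90% CI is slightly broader than the BE criteria, individual AUC and".

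Neither document gives a number for slightly broader, says which limit must be breached, sets an upper value for the ratio, or says whether 'individual' means each parameter or each participant.

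**The concern.** The primary rule guards against a fall and a rise in OC exposure, each at 5%. The fallback opens when that rule fails on either side but checks only for a fall. If it is reached because the upper limit exceeded 125%, it does not look at the problem that opened it. A rise in EE or LN exposure that fails the plan's own 125% limit could then be reported as no clinically significant interaction.

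This is separate from the undefined word slightly and from the missing confidence bound on 0.7. Requiring the lower confidence limit, rather than the point estimate, to exceed 0.7 would change nothing on the upper side, because that limit is already at least 0.80.

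**Working it through.** **Inputs.**
- Acceptance range 0.80 to 1.25 and fallback value 0.7: SAP 9.1.
- Planning values "for a type-I error of 0.05 and an intra-subject coefficient of variation of 16" per cent, with an expected ratio that "is included in the range [0.90, 1.10"]: SAP 2.3.
- SAP 2.3 also cites a CV of 10% for the AUC of EE and LN and for LN Cmax; 16% is for EE Cmax.
- N = 14, 7 per sequence: SAP 2.2. SAP 1 restricts reporting to Part 1.
- Assumption, not in the documents: slightly broader is taken to mean an upper limit of at most 1.30, 1/0.75 = 1.33, or 1/0.70 = 1.43.

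**Model.** 2x2 crossover on the log scale: s = sqrt(ln(1+CV²)), SE = s·sqrt(2/N), df = N−2, 90% CI = ratio ×/÷ exp(t(0.95, df)·estimated SE). Probabilities are integrated over the distributions of the estimated ratio and the estimated variance.

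**The plan's own figures.** At ratio 0.90 and CV 16%, N = 26 gives 82.9% power (N = 24 gives 79.99%) and N = 34 gives 91.1%. The stated 26 for 80% and 34 for 90% reproduce.

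**Why the group check cannot fail on the upper side.** The estimated ratio is the geometric midpoint of its CI, sqrt(L·U). With L ≥ 0.80 and U > 1.25 it exceeds sqrt(0.80 × 1.25) = 1.00, so it exceeds 0.7. This holds for any N and CV.

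**Example.** At N = 14 and CV 16%: s = sqrt(ln 1.0256) = 0.159; SE = 0.159 × sqrt(2/14) = 0.0601; t = 1.782; CI factor = exp(1.782 × 0.0601) = 1.113. The upper limit passes 1.25 once the observed ratio exceeds 1.25/1.113 = 1.12. An observed ratio of 1.16 has a CI of 1.16/1.113 = 1.04 to 1.16 × 1.113 = 1.29. It fails the primary rule. If 1.29 is called slightly broader, it passes the fallback.

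**Probability of a favourable declaration, one parameter, N = 14, group-ratio reading.**

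| True ratio, CV | Primary rule | Cap 1.30 | Cap 1.33 | Cap 1.43 |
|---|---|---|---|---|
| 1.25, 16% | 5% | 15% | 26% | 67% |
| 1.25, 10% | 5% | 25% | 49% | 95% |
| 1.30, 16% | 1% | 5% | 11% | 43% |

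Simulation agrees to within about one percentage point.

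**How often an upper-side breach arises, one parameter, N = 14, CV 16%.** About 0.02% at true ratio 0.90, 3% at 1.00 and 36% at 1.10.

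**Per-participant reading.** Suppose instead that every participant's ratio must exceed 0.7. Given an upper-side breach (N = 14, CV 16%), the check passes in about 65%, 80% and 94% of trials at true ratios 1.00, 1.10 and 1.25. It can fail, but it becomes easier to pass as exposure rises.

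**The case against.** A reader might infer that every result passes, or that a rise of any size would be declared harmless. The text does not support that. The fallback admits only intervals slightly broader than 80% to 125%, so a gross excess is outside its wording. The word has no number, so the boundary is left to judgement, but it is not absent. With a cap of 1.30, 85% of trials at a true ratio of 1.25 (CV 16%) still do not pass. The larger figures need a cap of 1.43, which is hard to call slight.

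The claim that the check cannot fail also depends on the reading. Protocol 9.3 and SAP 9.2 use 'individual' for participant-level AUC ratios, and on that reading failure is possible. The group reading fits better, because the sentence speaks of geometric mean ratios, but the text does not settle it. Neither reading supplies an upper limit.

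The strongest point is direction. The documents describe PSL as a weak CYP3A4 inducer. Midazolam exposure fell by 44% at 400mg BID, the model in Protocol 2.1 predicts a 16% fall in EE AUC, and the Part 2 power statement assumes a 10% fall. True ratios of 1.25 or 1.30 are not expected effects. This explains why the limit is 0.7. It does not explain why the fallback should also serve breaches of the opposite limit, and the plan's own planning range runs up to 1.10.

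Two further limits stand. The percentages are for one parameter, whereas SAP 2.3 requires AUC and Cmax of both analytes. The labeling consequence is weakened, because SAP 1 says that the epilepsy project was terminated and that only a subset of Part 1 outputs will be reported. The ratio and its 90% CI are to be provided under SAP 9.1, so a rise would be visible to anyone who reads the estimate rather than the conclusion.

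**Conclusion.** The point holds in a limited form. The fallback is not confined to the 80% side and has only a lower limit. On the group-ratio reading, any upper-side breach accepted as slightly broader passes automatically; on the per-participant reading it may fail, but nothing limits a rise. At a true ratio of 1.25 (one parameter, N = 14, CV 16%), the 5% chance of a favourable declaration becomes roughly 15% to 67%, depending entirely on the assumed meaning of slightly broader. The practical weight is moderate, because a breach on this side is very rare if exposure falls as expected and becomes common only near the top of the planning range. The documents do not support the stronger inference that every upper-side result passes. Even so, this is a stated decision rule that can give the wrong conclusion on one side, not merely a missing detail.

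**What to change.** In SAP 9.1, state that the >0.7 fallback applies, parameter by parameter, to the group geometric mean ratio, and only when the lower 90% limit is below 80% and the upper limit is at or below 125%. If the upper limit exceeds 125%, lack of interaction is not concluded and the ratio is reported with its 90% CI. Record the change in SAP 3.9, since Protocol 9.3 has the same wording, and align the protocol if it is amended again.

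**Cost.** A short SAP amendment before database lock, which SAP 1 already provides for. No new data or analysis is needed. The price is that a chance breach of the upper limit can no longer be rescued: about 3% of trials per parameter at a true ratio of 1.00, and up to 36% at 1.10 (CV 16%, N = 14). A CI that is too wide on both sides is also barred; at N = 14 and CV 16% that needs an estimated SE about ln 1.25 / ln 1.113 = 0.223/0.107 = 2.1 times the planned one. The change does not define slightly broader on the lower side, which still needs a number.
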